The use of JUVÉDERM VOLUMA™ XC in the temporal areas of the face will show an improvement of ≥ 1 grade as compared to pre-treatment by a trained investigator and the subject's satisfaction with their appearance will improve by ≥ 1 grade as compared to pre-treatment scores. The investigator will assess the treated patients using the Temporal Fossa Rating scale (see Appendix A). The risk of mild adverse side effects is expected to be less than 5 percent, with no expected incidences of moderate to severe adverse events.

DESIGN

This study will be an open label, single center study, composed of a treating investigator and 30 subjects.

30 subjects will be injected with JUVÉDERM VOLUMA™ XC to their right and left facial temporal regions at the baseline visit. Subjects will receive up to 4, 1mL syringes of JUVÉDERM VOLUMA™ XC for their initial injection and a maximum of 6, 1mL syringes of JUVÉDERM VOLUMA™ XC for the study. Subjects will undergo one touch-up injection approximately 2 weeks post initial treatment, and will continue to be evaluated at month 1, month 3, and month 6. All treated subjects with the study product may exit the trial at month 6.

The baseline visit will consist of completion of the informed consent, medical history, concomitant medications and procedures, pregnancy screen via urine pregnancy test (females of child bearing potential only), and evaluation of both inclusion and exclusion criteria. Upon determination of qualification for study participation, subject's assessments (see Appendices C and E), investigator assessments, and photography will be completed. Subjects will proceed to

the initial injection, if no wash out is required. The treating investigator will inject a maximum of 4, 1mL syringes of JUVÉDERM VOLUMA™ XC into the subject's facial temporal area (see Figure 1). Treating investigator may use ice packs to diminish swelling prior to; or post injection. After the initial treatment, subjects will receive a treatment diary (see Appendix F) spanning from initial treatment to touch up treatment in order to monitor treatment site, patient reaction to study product and comments. The diary will be completed daily post-injection for 14 days post each injection. Treated subjects will undergo photos post-treatment as well. Subjects will receive a phone call three days post-treatment for a follow up.

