Have a history of migraines or frequent headaches, as determined by the PI.
Have blindness or partial vision loss in either eye.
Have received any other therapy, which, in the opinion of the investigator, could interfere with safety or efficacy evaluations.
Current enrollment in an investigational drug or device study or participation in such a study within 30 days of entry into this study.
Patient who has a condition or is in a situation that, in the investigator's opinion, may put the patient at significant risk, or may significantly interfere with the patient's participation in the study.
Have received anti-coagulation, anti-platelet, or thrombolytic medications (e.g., warfarin), anti-inflammatory drugs (NSAIDs, e.g., aspirin, ibuprofen), or other substances known to increase coagulation time from 10 days pre- to 3 days post injection. A wash out period of 10 days is allowed.
Have undergone immunosuppressive therapy, chemotherapy, biologics or systemic corticosteroids within 3 months prior to each study visit.

DRUG DISPENSING

A total of 30 subjects will be treated with JUVÉDERM VOLUMA™ XC.

The JUVÉDERM VOLUMA™ XC study products will be placed in a locked temperature monitored study cabinet for the duration of the trial. On treatment day, Baseline/Visit 1, subjects will receive a treatment of a maximum of 4 total, 1 mL syringes of JUVÉDERM VOLUMA™ XC. Maximum drug allotted per subject including initial treatment and touch up treatment will be 6, 1 mL syringes.

SCREENING/ VISIT 0

Before enrollment into the study, subjects must sign the informed consent form and the HIPAA form. Once the subject has signed the informed consent and HIPAA, the following procedures will be conducted:

- Inclusion and exclusion criteria will be reviewed.
- Demographic information will be recorded.
- Medical/surgical history and concomitant medications will be obtained from the subject and recorded.
- Physical exam will be performed including vital signs and visual assessments
- The investigator will rate the subject's facial temporal areas using a scale with photo guide as follows (1 = Convexity, 2 = Flat, 3 = Mild Concavity, 4 = Moderate Concavity, and 5 =Severe Concavity). This scale will be referred to as the Frontal Temporal Fossa Rating Scale.
- Inclusion and exclusion criteria will be reconfirmed
- Subjects who do not meet the inclusion and exclusion criteria will be marked as screen failures

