- A diary will be dispensed for subjects to record any reaction to study product or comments prior to Visit 2. Subjects will be instructed on diary completion
- The treating investigator will review the Vision Test results, compare to baseline and examine the patient prior to dismissal.
- Subjects will be instructed to contact the office if they experience any unexpected side effects including intense pain of the skin, eye pain, or visual disturbances. In case of an emergency, subjects will be instructed to call 911.

DAY 3 POST INITIAL TREATMENT FOLLOW UP PHONE CALL (±1 DAY)

- Subjects who received treatment will be called and questioned about AEs, SAEs, changes in concomitant medications, or concomitant procedures.
- Subjects will be reminded to complete study diary and call the office if any issues may arise.
- Subjects will be reminded of exclusionary concomitant medications/procedures.

VISIT 2/WEEK 2 FOLLOW UP/ POSSIBLE TOUCH UP/ (±3 DAYS)

Treated subjects will come for a follow up at week 2 (±3 days) after initial injection. The following procedures will be conducted:

- Study diary will be collected and reviewed.
- Changes in adverse events and concomitant medications/procedures will be documented.
- Subject’s vitals and weight will be documented.
- The Vision Test will be administered on the iPad.

- Physical exam will include a visual field analysis
- Photos using the Canfield VISIA camera will be taken.
- Treatment subjects will complete the assessments.
- If Treating Investigator determines a touch-up is indicated, then perform the following:
 - Subjects' vital signs will be taken
 - Touch up will be performed by the treating investigator. The combined initial treatment and touch up treatment drug total per subject will not exceed 6cc (six 1 mL syringes) of JUVÉDERM VOLUMA™ XC.
- Subjects may receive ice packs to reduce swelling and bruising post-treatment. Any actions taken will be documented.
- Monitor treatment subject for at least 15 minutes post injection.
- The Treating Investigator will review the Vision Test results, visual field exam and compare to baseline results and examine the patient prior to dismissal.
- A diary will be dispensed to subjects to record any reaction to study product or comments for collection at the month 1 visit.

Subjects will be scheduled for the next visit and reminded to complete their diaries and return them at the next visit

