- Treating investigator will rate the subject's treatment area using the Temporal Fossa Rating Scale, Investigator's Satisfaction with the Appearance of the Temporal Regions, and the Subject Global Aesthetic Improvement Scale (GAIS)
- Subjects will exit the study

DATA ANALYSIS, MONITORING, AND STORAGE

Data analysis and monitoring will be performed on safety and efficacy of all subjects who are randomized into the study. Descriptive statistical methods will be used to summarize subject population and demographic characteristics.

All study-related documents, such as correspondence, regulatory documents, consent forms and source documents will be kept confidential. Only authorized research staff will have access to the documentation, which will be stored in a secure area.

ANTICIPATED ADVERSE EVENTS

Any adverse events that occur during the study that may or may not have a relationship with the study treatment must be reported for all subjects. Some adverse events that have been observed or reported after JUVÉDERM VOLUMA™ XC injections consist of the following:

- Itching
- Redness
- Pain
- Lumps/Bumps
- Infection at injection site
- Allergic reaction
- Unsatisfactory/unsymmetrical result
- Nausea
- Headache
- Blood vessel injury
- Skin ulceration or necrosis
- Telangiectasia
- Vision disturbances as serious as blindness

In addition, the following adverse reactions have been observed at the injection site:

- Redness
- Nodules
- Bruising
- Pain
- Inflammation
- Numbness
- Needle marks
- Infection

All adverse events will be recorded in source (see Appendix F) and will be assessed by the principal investigator. The investigator will document any actions required. The principal investigator will also determine the severity and causality for adverse events. All adverse events which remain “ongoing” at the exit visit will be followed-up as appropriate.

Information about adverse events reported in the study will be aggregated and summarized. Adverse events information will be collected via subject report and investigator observation at each visit and monitored by the investigator. The rates of adverse events in each treatment group will be compared. An investigator will determine causality of adverse events, and all adverse events will be reported to the Institutional Review Board (IRB) according to policies and procedures.

SERIOUS ADVERSE EVENTS

A serious adverse event will consist of any medical condition with the following outcomes:

- Resulted in death

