Appendix F

Subject Diary Day 0-14

Day _____ Date _____

Treatment Response Events	Left Side				Right Side				Comments
	None	Mild	Moderate	Severe	None	Mild	Moderate	Severe	
Redness/ dermatitis									
Pain / tenderness of skin									
Skin discoloration									
Lumps/ Bumps									
Swelling of injection site									
Bruising									
Itching									
Nausea									
Headache									
Dizziness									
Eye Pain									
Blurred vision									
Decreased vision									
Other (specify)									

Key to terms:

None = not present

Mild = noticeable but does not interfere with daily activity and did not require medication or treatment

Moderate = bothersome and/ or required medication or treatment or was disruptive to normal routine

Severe = sought medical attention and was disruptive to normal routine

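### The symptom checklist is first used after injection, so in a single-arm study with both temples treated, symptoms a subject already had cannot be told apart from those that began afterwards

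*Combined protocol and SAP*

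**What the plan says.** The DESIGN section describes one treated group: "This study will be an open label, single center study, composed of a treating investigator and 30 subjects". Every subject is injected "to their right and left facial temporal regions at the baseline visit", so neither a second arm nor a second temple serves as a comparison.

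The Appendix F diary follows the injection: "After the initial treatment, subjects will receive a treatment diary (see Appendix F) spanning from initial treatment to touch up treatment". On its schedule the section adds: "The diary will be completed daily post-injection for 14 days post each injection". The Visit 1 list agrees: "A diary will be dispensed for subjects to record any reaction to study product or comments prior to Visit 2". The form is titled "Subject Diary Day 0-14" and has no pre-injection days. The telephone script (Appendix G) is used on day 3 after treatment.

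Before injection, the subject completes Appendices C and E, on satisfaction and perceived age. Screening takes a general history ("Medical/surgical history and concomitant medications will be obtained from the subject and recorded"), a physical exam and visual assessments. The Vision Test is done before and after injection at Visit 1 and again at week 2, and the results are compared with baseline.

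Under ANTICIPATED ADVERSE EVENTS, events "that may or may not have a relationship with the study treatment must be reported for all subjects", and the principal investigator judges severity and causality. CLINICAL HYPOTHESIS expects mild side effects in under 5% of subjects and no moderate to severe events.

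**The concern.** Appendix F has 13 named items. Six of them can occur in people who have had no injection: itching, nausea, headache, dizziness, eye pain and blurred vision. A subject who has one of these on the morning of treatment and still has it on day 2 enters it in the diary just as a subject whose symptom began after injection does. The form's column heading treats every row as a response to treatment.

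This matters because ENDPOINTS puts safety in the primary endpoint, and because eye pain, dizziness and nausea are the symptoms that the background section links to visual injury. The efficacy scales have a matched baseline; these symptoms do not. The one planned safety comparison, between treatment groups, cannot be made with a single group. A pre-injection record is therefore the only reference the study could have for these items.

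**Working it through.** **What is recorded before and after injection**

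| Item | Before first injection | After |
|---|---|---|
| Satisfaction, perceived age | Appendices C and E | same forms |
| Visual acuity on visit days | Vision Test | Vision Test, compared with baseline |
| Itching, nausea, headache, dizziness, eye pain | general history only; items not asked | daily diary, day 3 call |
| Blurred vision between visits | not asked | daily diary, day 3 call |

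The gap lies in the last two rows.

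**Inputs for an illustration.** n = 30 (DESIGN). Expectations: under 5% mild, no moderate to severe (CLINICAL HYPOTHESIS). The 5% has no derivation, so there is nothing to reproduce; in subjects it is 0.05 × 30 = 1.5. One affected subject is 1/30 = 3.3%, below the figure; two are 2/30 = 6.7%, above it. The documents give no background rate. Let b be the assumed chance that a subject has at least one of these symptoms in a 14-day window, with zero filler effect.

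**Step 1: background symptoms in the diary.** Expected subjects = 30b. P(2 or more) = 1 − (1 − b)^30 − 30b(1 − b)^29. At b = 0.10 this is 1 − 0.0424 − 0.1413 = 0.816.

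| b | Expected subjects | P(2 or more) |
|---|---|---|
| 1% | 0.3 | 3.6% |
| 2% | 0.6 | 12.1% |
| 5% | 1.5 | 44.6% |
| 10% | 3.0 | 81.6% |
| 20% | 6.0 | 98.9% |

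These figures show what having no control arm costs. They include symptoms that arise by coincidence after injection, which a baseline form does not remove.

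**Step 2: what a pre-injection record removes.** Let r be the chance that a subject with a background symptom in the diary window also had it, at the same or a higher grade, in the 14 days before. The new-or-worsened count then has probability b(1 − r). If symptoms are episodic and independent between windows, r = b. If they are fully persistent, r = 1 and none remain.

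| b | b(1 − b) | Expected subjects left if episodic | P(2 or more) left | Subjects removed: episodic to persistent |
|---|---|---|---|---|
| 5% | 4.75% | 1.43 | 42% | 0.075 to 1.5 |
| 10% | 9% | 2.7 | 77% | 0.3 to 3.0 |
| 20% | 16% | 4.8 | 96% | 1.2 to 6.0 |

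**Step 3: the moderate to severe expectation.** Appendix F grades a symptom moderate if it needed medication, so one ordinary headache treated with a tablet contradicts an expectation of none. P(at least 1 of 30) = 1 − (1 − b)^30, where b is now the assumed background rate of such an event: 45% at 2% and 79% at 5%. Here too, the record helps only where the symptom was already present at that grade.

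**The case against.** The plan is not without safeguards. Acuity has a before-and-after test. The exclusions cover migraine and frequent headache, uncontrolled systemic disease, named and uncontrolled eye disease, partial vision loss, multiple allergies, and dermatitis in the treatment area. The diary is daily, graded and by side, and the background section describes eye pain from visual injury as immediate, so timing helps attribution. The principal investigator judges each event. All of this stands. It lowers the background and helps with single cases, but the judgement is unblinded and has no symptom record from before injection to draw on.

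A reader might infer that the plan inflates the adverse event rate. The documents do not support that. An all-causality count properly includes background events. It misleads only if the entries are read as filler effects or set against the under-5% figure, and the documents do not say which count that figure uses. The direction of any bias in the related-event count is not established either, since an unblinded injector could also under-attribute.

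The under-5% figure is an expectation, not a success criterion or stopping rule. Bruising, swelling and tenderness, which the protocol names among the most common events, could exceed 1 of 30 with no background symptoms at all. Crossing 5% would therefore say little about this gap.

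Finally, the gain from a baseline form is small if symptoms are episodic, as Step 2 shows. That is a fair reason not to oversell it.

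**Conclusion.** The point holds in a limited form. For itching, nausea, headache, dizziness, eye pain and blurred vision between visits, the study cannot separate symptoms a subject already had from those that began after injection. This follows from the text alone and needs no assumed rate. The wider reading, that blurred vision in general has no reference, fails because acuity on visit days is compared with a pre-injection Vision Test.

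The size cannot be derived from the documents. Under the assumed background rates of 5%, 10% and 20%, with zero filler effect, 1.5, 3 and 6 subjects of 30 would record a symptom. A pre-injection record would remove between 0.075 and 1.5, 0.3 and 3, or 1.2 and 6 of them, depending on how persistent the symptoms are. The exclusions remove some chronic sufferers, which points away from the upper ends. The change is worth making because it is cheap and because a baseline not taken before injection can later be rebuilt only from memory. It does not replace a control group.

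**What to change.** Add one step to the Visit 1 list, before the first injection: the subject completes the Appendix F items once, by side, for that day and for the previous 14 days, using the same grades. In the adverse event table, show events that are new or worsened in grade against that record beside the all-events count. State in CLINICAL HYPOTHESIS which of the two counts the under-5% and no moderate to severe expectations refer to.

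Use the same pre-first-injection record as the reference for the touch-up diary. Taking the last entry of the first diary instead would make a post-injection day the baseline, and a persisting symptom caused by the filler would no longer be flagged after re-injection.

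The cost is one extra page on an existing form and one table column. Recall over 14 days is less exact than a daily diary, so the all-events count should stay. The record deals only with symptoms already present; new coincidental ones still cannot be attributed without a control, and the report should say so.

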Hyaluronidase will be injected into the temple area in the area of Voluma injection or ischemia. 0.5- 1.0 cc will be used per ischemic site. Only the affected areas will be treated. After injection of hyaluronidase, the injected area will be massaged. If the filler has migrated to a distant location, the hyaluronidase will be injected in the area where the vessel appears to be ischemic and the surrounding vascular area will be massaged for 2 minutes to encourage penetration of the hyaluronidase into the vessel. A warm compress may be used to increase blood flow to the area. Nitropaste should only be used in patients with no history of heart disease. After application of nitropaste, if the patient feels dizzy, vital signs should be taken and the patient should be given juice. If blood pressure drops below 90/60, the nitropaste should be removed immediately and the patient's blood pressure should be closely monitored. If it does not rise in 5 minutes and the patient continues to feel dizzy or unwell, 911 will be called. If visual disturbances persist- the patient will be transferred to the Bascom Palmer ER. If the ischemia persists, the Pi will decide if the patient needs to go to the ER or if the ischemia is mild (and not affecting vision) the patient will be placed on one aspirin every 4 hours, and warm compresses and seen within 18 hours by the PI to check for revascularization. NOTE: THE PATIENT WILL NOT BE PLACED ON ASPIRIN IF A VISUAL DISTURBANCE OCCURS IN CASE SURGICAL INTERVENTION IS NECESSARY.

Summary of background

Hyaluronic acid injections have been used safely in the temples in many patients by many physicians, including [name]. Risks, however, do exist but do not seem to be as common as in patients treated with HA fillers in the nasolabial folds. Clinical studies using JUVÉDERM VOLUMA™ XC have demonstrated efficacy, safety and duration of the dermal filler in the mid-facial area. Many doctors are advocating the use of VOLUMA™ in the temples, therefore, there is a need to conduct clinical studies of augmentation in the temporal regions of the face in order to develop an approach that mitigates risk and management of adverse events. The purpose of this study is to evaluate efficacy and safety using a cautious injection technique with a clear plan for recording and treating adverse events.

STUDY DESIGN

CLINICAL HYPOTHESIS

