Subjects will return two weeks post initial injection for a possible touch up. The treating investigator will determine whether a touch up treatment is necessary. Prior to treatment, subject diaries will be collected and reviewed. All AEs/SAEs, changes in concomitant medications and concomitant procedures will be documented. Per the treating investigator's discretion, the subject may or may not qualify for a touch up. The subject will undergo photos. If treatment is necessary, subject will undergo same procedures as the initial injection visit. Post-treatment photos will be taken and subject will receive another diary and 3 day post injection phone call.

Follow up visits will consist of documentation of AEs/SAEs, changes in concomitant medications and changes in concomitant procedures at the beginning of the visit. The investigator and subject will complete their respective assessments and photos will be taken.

ENDPOINTS

The primary endpoint of this study is to determine the efficacy and safety of JUVÉDERM VOLUMA™ XC when used in the facial temporal regions based on the change in the score of the investigator's Temporal Fossa Scale. The secondary endpoints are the 2-point change in the scale of Subject's Satisfaction of Facial Appearance and Investigator's Satisfaction Scale.

STUDY PROCEDURES

PROCESS OF CONSENT/SUBJECT COMPREHENSION

All subjects will first be given the informed consent to read over by themselves. One of the investigators and a qualified member of the research staff will then review the informed consent with the prospective subject. The subject will then be allowed ample time to ask any questions about the study, and all questions will be answered. The person obtaining consent will ensure that the subject has a clear understanding of the study procedures. Once all questions are answered and the subject chooses to enroll in the study, the subject will be asked to sign the IRB-approved informed consent document. No study procedures will be conducted prior to signing the informed consent. Each subject will receive a copy of their signed informed consent for their information.

CONSENT FORMS

IRB approval will be obtained prior to use of the consent form.

INCLUSION CRITERIA

Subjects must meet the following inclusion criteria to be enrolled in this study:

Be willing and able to read and sign the informed consent and other study documents.

Male or female, 35- 75 years old.

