If subjects report any unexpected side effects at this visit or at any time after injection, they will be scheduled to come to the office for evaluation.

DAY 3 POST TOUCH-UP TREATMENT FOLLOW UP PHONE CALL (±1 DAY)

- Subjects will be called and questioned about AEs, SAEs, changes in concomitant medications, or concomitant procedures.
- Subjects will be reminded to complete study diary and call the office if any issues may arise.
- Subjects will be reminded of exclusionary concomitant medications and procedures.

VISIT3 /MONTH 1(±7 DAYS)

At this visit(s), the following procedures will be conducted:

- Changes in adverse events and concomitant medications will be documented.
- Subject's vitals and weight will be documented.
- Photos using the VISIA will be taken.
- Subject will complete the following assessments:
 - Subject's Satisfaction with Temple Appearance
 - Subject Self-Perception of Age
- Treating investigator will rate the subject's treatment area using the Temporal Fossa Rating Scale, Investigator's Satisfaction with the Appearance of the Temporal Regions, and the Subject Global Aesthetic Improvement Scale (GAIS)
- Subjects will be scheduled for next visit.

- Subjects will be scheduled for next visit.

VISITS 4,5,6 /MONTH 3,6,and 9 (±7 DAYS)

At this visit, the following procedures will be conducted:

- Changes in adverse events and concomitant medications will be documented.
- Subject's vitals and weight will be documented.
- Photos using the VISIA will be taken.
- Subject will complete the following assessments:
 - Subject's Satisfaction with Temple Appearance
 - Subject Self-Perception of Age
- Treating investigator will rate the subject's treatment area using the Temporal Fossa Rating Scale, Investigator's Satisfaction with the Appearance of the Temporal Regions, and the Subject Global Aesthetic Improvement Scale (GAIS)
- Subjects will be scheduled for next visit.

If subjects report any unexpected side effects at these visits or at any time after injection, they will be scheduled to come to the office for evaluation.

VISIT 7/MONTH 12- STUDY EXIT (±7 DAYS)

At this visit, the following procedures will be conducted:

- Changes in adverse events and concomitant medications will be documented.
- Subject's vitals and weight will be documented.
- Photos using the VISIA will be taken.
- Subject will complete the following assessments:
 - Subject's Satisfaction with Temple Appearance
 - Subject Self-Perception of Age

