Appendix A

Frontal Temporal Fossa Rating Scale

Please grade severity of the temporal line of the frontal bone (TLFB) using the Frontal Temporal Fossa Rating Scale: (these will have a picture assigned to each score. Pictures are currently being collected).

Score (Circle One)	Description	
5	Severe Concavity	Severe recess of the tissue below the temporal line of the frontal bone; TLFB very prominent
4	Moderate Concavity	Moderate recess of the tissue below the plane of the temporal line of the frontal bone; easily visualized; TLFB mildly prominent
3	Mild Concavity	Mild recess of the tissue below the plane of temporal line of the frontal bone; TLFB visible
2	Flat	Temporal line of the frontal bone not visible or slightly visible
1	Convexity	Tissue extends beyond the plane of the temporal line of the frontal bone (TLFB); TLFB not visible

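### The primary endpoint reads safety from a temple-contour score, and the planned between-group comparison of adverse events cannot be run in a single treated group of 30

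*Combined protocol and SAP*

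**What the plan says.** All places are in the combined protocol and SAP.

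- **Purpose.** Summary of background: "The purpose of this study is to evaluate efficacy and safety using a cautious injection technique".
- **Primary endpoint.** Endpoints, with one measure for both aims: "efficacy and safety of JUVÉDERM VOLUMA™ XC when used in the facial temporal regions based on the change in the score of the". What is scored there is the Temporal Fossa scale, as rated by the investigator. Both secondary endpoints are satisfaction scales.
- **What the scale grades.** Screening/Visit 0: "1 = Convexity, 2 = Flat, 3 = Mild Concavity, 4 = Moderate Concavity, and 5 =Severe Concavity". Appendix A describes each grade by tissue contour; grade 5, for example, is "Severe recess of the tissue below the temporal line of the frontal bone; TLFB very prominent".
- **Safety expectation.** Clinical Hypothesis, on adverse events: "The risk of mild adverse side effects is expected to be less than 5 percent, with no expected incidences of moderate to severe". No source or counting unit is given.
- **Design.** Design and Drug Dispensing: one centre, open label, 30 subjects, all given the product.
- **Analysis.** Data Analysis, Monitoring, and Storage covers subjects who are randomized and names descriptive methods only for population and demographics. Anticipated Adverse Events says that adverse events will be pooled and summarised, and that their rates will be compared across treatment groups. It also says that adverse events are recorded in source, pointing to Appendix F, which is the subject diary.
- **Time frame.** Design: "The diary will be completed daily post-injection for 14 days post each injection", and "All treated subjects with the study product may exit the trial at month 6". The visit schedule, however, continues to "VISIT 7/MONTH 12- STUDY EXIT (±7 DAYS").

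**The concern.** Safety is half of the stated purpose and half of the primary endpoint, but the measure attached to it is cosmetic contour. A subject could move from grade 4 to grade 2 and have an arterial occlusion, and the primary endpoint would record a success. The secondary endpoints do not fill the gap.

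The analysis text does not repair this. Its one specific instruction for adverse events needs at least two groups. Without it, the reader has an instruction to summarise but no rule on the unit, on how severity and causality enter the table, on whether diary reactions count, or on the period covered. Those choices could be made after the data are seen, and the diary choice could move the headline proportion a long way. It is also unstated how much, or how little, a result of zero events in 30 would show.

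**Working it through.** **Inputs**

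- n = 30 treated subjects (Design; Drug Dispensing).
- Expectation of under 5% mild events and none above mild (Clinical Hypothesis).
- Arterial occlusion in fewer than 2% of patients (Uncommon adverse events). This is for HA filler generally; the section says it is seen most often in nasolabial and glabellar injection.
- Assumptions of this review: the unit is the subject, subjects are independent, and confidence is 95%. The documents state no unit for the rates and no confidence level.

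**The plan's own figure.** The 30 cannot be reproduced. No alpha, power, effect size, reference rate, dropout allowance or interval width is given.

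**Passages side by side**

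- Endpoint against scale: every grade in Screening/Visit 0 and Appendix A is a description of contour. None mentions a reaction, an occlusion or vision.
- Comparison against design: with one group, a difference or ratio of rates between groups is undefined. The word randomized can only mean the 30 treated subjects.
- Exit: month 6 in Design, month 12 in the visit schedule. The Inclusion Criteria require no plan to move from Miami for 12 months.
- Severity: the diary key (Appendix F) counts disruption of normal routine as a route to Moderate; the telephone key (Appendix H) does not.

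**Precision with zero events.** P(0 events) = (1 − p)^30. Setting this equal to the tail probability and solving for p gives the exact (Clopper-Pearson) upper limit:

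- one-sided 95%: 1 − 0.05^(1/30) = 0.0950, or 9.5%
- two-sided 95%: 1 − 0.025^(1/30) = 0.1157, or 11.6%

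Both exceed 5%, so even zero events in 30 leaves a 5% rate inside the interval.

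**Precision with one event.** 1/30 = 3.3%, with an exact two-sided 95% interval of 0.1% to 17.2%.

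**Arterial occlusion.** At the 2% ceiling, P(none in 30) = 0.98^30 = 0.5455, or 54.5%. At a lower true rate a clean result is more likely still; at 1%, assumed for illustration, it is 0.99^30 = 0.740.

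**The case against.** The strongest reply is that safety is well covered elsewhere, and much of that stands. The UADE section lists blindness, visual field loss and confirmed acuity loss, and any of them halts enrollment. The Clinical Hypothesis separates mild from moderate-to-severe events. Appendices F and H define grades, and the principal investigator assigns severity and causality. Collection is scheduled through diaries, day-3 calls and visits. A reader might infer that safety is ignored, or that no safety outcome appears anywhere. The documents do not support that. The gap is narrower: none of these items is carried into the endpoints or given a tabulation rule.

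A second reply is that the expectation has some basis. The background reports roughly 40 VOLUMA and 80 JUVÉDERM temple patients with nothing beyond mild, temporary swelling and bruising, and Common adverse events says the temple tends to bruise and swell less than other areas. This is uncontrolled experience. It supports the absence of events above mild but gives no rate of mild events. A reader might also infer that the under-5% figure is bound to be missed, because the same section lists bruising and swelling among the most common reactions. That does not follow either: the list is a ranking, and no mild-event rate is given.

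A third reply is that a small descriptive study needs no power calculation. Agreed. The figure is an expectation, not a test, and the intervals above do not show that 30 is too few for a descriptive purpose.

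Finally, a comparison that cannot be run cannot give a wrong answer. True, but once it is removed no defined safety analysis remains.

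**Conclusion.** The point holds. The endpoint sentence and the between-group comparison are wrong as written: the first ties safety to a measure that cannot detect harm, and the second has no second group. The remaining instruction to summarise adverse events lacks a tabulation rule and an interval.

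The size is best put as what 30 subjects can show. Zero events excludes only rates above about 11.6% (two-sided 95%) or 9.5% (one-sided). At the protocol's own 2% ceiling for occlusion, no case would be seen more often than not (54.5%). These figures assume counting by subject, all 30 evaluable, and 95% confidence; the 2% is not specific to the temple. The documents do not establish that the safety expectation is false or that the trial needs more subjects.

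**What to change.** 1. In Endpoints, limit the Temporal Fossa endpoint to efficacy.
2. Add a descriptive, subject-level safety endpoint from data already collected: the number and proportion of treated subjects with any adverse event, by severity and by relationship to the device, plus arterial occlusion and the visual events listed in the UADE section, each with an exact 95% confidence interval.
3. State whether Appendix F diary reactions count as adverse events, and show the proportion with and without them. Use the 14 diary days after each injection for diary reactions, and first injection to study exit for other events. The sponsor must first reconcile the month 6 and month 12 exits, with the 12-month residence criterion in view.
4. In the analysis text, change randomized to treated, and replace the between-group comparison with this single-arm summary.
5. Give the source and unit of the under-5% figure or delete it, and state that 0/30 excludes only rates above about 11.6% (two-sided 95%).
6. Reconcile the two Moderate definitions in Appendices F and H, since the table is by severity.

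The enrollment halt is unaffected. The cost is wording, a little descriptive analysis and a less favourable safety statement. No subjects, visits or procedures are added.
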